## **Device Description**

SU-VEID is a vein entry indicator device. The device is an electronic and algorithm-controlled pressure sensitive device, tiny, and integrated to flash chamber of an IV catheter. The device signals by beeps and lights instantly when entering the vein lumen and continues signaling as long as the tip of the needle is within the vein. After exiting the vein (either backwards or forward), once the tip of the needle re-enters the vein, the device signals again. Hence the device is an aid for venous lumen entry and alerts the clinician if the needle strays outside the lumen during the insertion process. The auditory feedback is overt, faster and more sensitive than the venous pressure/ capillary action required to see blood in the flash chamber. Moreover, the device allows the clinician to focus their vision on the insertion technology (ultrasound screen or NIR field), rather than divide it between that and the flash chamber. Therefore, it is believed that it will improve stick success.

## SU-VEID attached but not activated

### BACKGROUND

#### **Problem worth solving**

Every year in US, hundreds of millions of IV placements are conducted. Nurses and Physicians experience the difficulties and the stresses which are involved with vascular access. Improving first attempt success is an important goal which will reduce vessel injury, pain of multiple insertions, reduces the risk of catheter related blood infections, risk of staff needle stick injuries, cost and increases patient satisfaction.

#### **Clinical Benchmark**

IV Start average number of attempts is  $>2$  in general population, and  $\geq 3$  attempts in difficult venous access patients.  
IV placements failures are up to 50% of the time before the IVs reach the end of their intended use.

#### **Clinical Background**

Venipuncture may be utilized for intravenous therapy or for sampling of venous blood. In human medicine, this procedure may be performed by a medical practitioner, for example a physician, a nurse, medical technician, a paramedic, or a phlebotomist,. Venipuncture is one of the most routinely performed invasive procedures and may be performed in order to obtain blood for diagnostic purposes, to monitor levels of blood components, to administer therapeutic treatments including medications, nutrition, or chemotherapy, and/or to collect blood for later uses, e.g., for blood donation, and more.

Venipuncture is performed by inserting a needle, such as an intravenous catheter into a blood vessel of the patient. For efficient performance of the procedure, the practitioner must have an indication when the needle enters and/or exits the vein. The most common indication is obtained by visual observation of the blood flowing from the vein through the needle to a flashback chamber or an associated reservoir (e.g., a syringe).

Intravascular catheter systems, such as peripheral intravenous catheters, are essential in modern medical practice. The conventional method of placing an IV catheter into a vein is using a catheter over-the-needle technique. Puncturing the skin with a needle catheter, moving the needle in surrounding tissues towards a targeted blood vessel, and puncturing the wall of the target vein provides a visual indication of blood within the flash chamber. Depending on the venous pressure and volume status, this indication of the needle being within the lumen of the vein can be variable, delayed or even falsely positive if the needle strikes the wall of the vessel again and goes outside of the lumen. All these scenarios contribute to missed IV placements and reduced first stick success.

Complications of incorrectly placed IV catheters include infiltration by medication administered in a high concentration to the local tissues around the vein instead of distributing in the blood system, causing hematoma, tissue damage, phlebitis, extravascular drug administration, thrombosis, delay of treatment, catheter related blood stream infection and loss of vein ultimately contributing to the patient being difficult vascular access.

Strategies to improve PIVC success with difficult venous access patients include devices such as ultrasound and other vein visualization technology. These devices have a significant learning curve and may produce poor results due to variability of skill level and the complexity of placement of IV catheters in patients with limited venous targets.

### **Description of the SU-VEID**

The SU-VEID is a sterile disposable device for indicating a position of the needle tip relative to a blood vessel of a patient, detecting and indicating entry of an intravascular catheter into a blood vessel. The device is configured to be attached to a proximal end of the catheter so that a lumen of the catheter is in continuity with the device, and the pressure of the blood or surrounding tissues is continuously measured using a pressure sensor of the device.

The device comprises: a pressure sensor configured to produce pressure values correlative to the surrounding pressure; a signal processor; an emitter configured to produce sound and an emitter configured to produce light. The pressure sensor responds to the changes in the pressure within the needle and activates a signal by an algorithm. The signal is indicated through simultaneous activation of the sound and light emitter. Accordingly, the device enables an instant identification of penetration by an intravascular catheter of both walls of a blood vessel by means of analysis of pressures history and changes in the pressure levels. The indications are instant, enabling the clinician to react instantly to the emitters signal, thereby avoiding double puncturing (infiltration). Furthermore, the indications are correlated to the state of the tip of the needle, i.e., a different indication signal is received while the tip of the needle is within the vein than when the tip of the needle is outside the vein.

The instant response also solves the problem of double penetration, i.e., crossing the distal wall of the vein, as in the case of double penetration the signal indication will cease. The cannula then needs to be slightly pulled back in position, until the signal is obtained once again without the cannula being removed from the patient's body. This increases the probability of completing and finalizing the procedure while the cannula is properly situated inside the vein.

### **Risk**

The SU-VEID is a low-risk device. The structure and principle of operation are such that the occurrence of adverse reactions is highly unlikely and hazard due to malfunction of the device is negligible.

The device interfaces with the existing procedure of catheterization of a blood vessel.

Worst Case Scenario, such as device failure, would not be predicted to impact PIVC as one would utilize the standard indication of the blood coming back into the needle.

Any adverse reactions reported by subjects or noted by study personnel will be recorded and reported.

A risk management and estimations were performed according to ISO 14971 (2007)

Further, SU-VEID does not interfere with the normal blood return into the flash chamber of the catheter so its use does not obstruct a clinician's normal cues of entry into the vein. What it does is identify the precise time of entry into the lumen even if the patient's volume status is low and blood refill into the catheter is slow. This should allow the clinician to reduce "back wall" injury of the vessel and hence increase success.

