Study Design	
1- General
 
 
a. SRNAs, CRNAs, and Physicians in the anesthesiology department who normally performs IV Starts as part of patient care may participate.
 
b. Study type: Prospective, Randomized Controlled Trial
 
 
2- Clinician Training
 
Each participating clinician will watch a training video and practice on a phantom to gain proficiency with the SU-VEID device prior to study participation.
 
3- The trial
 
 
- The potential intravenous catheter inserter will assess the difficulty of the IV start preoperatively
 
- Pre-surgical subjects requiring an IV without adequate visually visible veins on the arms will be considered difficult venous access and approached for consent.
 
- Subjects who are consented/ assent will be assigned a study number and randomized to either standard IV insertion or with SU-VEID by the research assistant
 
- The clinician will perform procedures with or without SU-VEID, according to the randomization scheme. To allow analysis across all clinicians, an individual clinician's participation will be limited to no more than 50% above/below the number of subjects that would occur if the subjects were distributed equally
 
 
4- A minimum of 200 subjects per control group and 200 subjects for the Study group.
 
 
- Subjects will be stratified to 200 (100 control, 100 SU-VEID) total using near infra-red vein (NIR) visualization and 200 (100 control, 100 SU-VEID) total using ultrasound (US) vein visualization. Targeting type I/II error rates of 0.05 and 0.2, respectively, this sample size would detect improvement of first pass success from 50% to 66%.
 

Study Groups	Pediatric patients in surgical pre-op (0-18 years old), requiring an I.V. catheter for surgery who are difficult venous access.

Study Population	
Inclusion
 
 
-Patient age <math>\leq</math> 18 requiring an IV for surgery who is difficult venous access
 
-Written informed consent/ assent from the patient or legal guardian.
 
 
Exclusion
 
 
-Patient age <math>></math> 18
 
-placement of the IV will be done according to standard operating room procedures, which typically is after induction of general anesthesia by mask
 

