### **Benefit**

Subjects may benefit by having the IV catheterization procedure performed with less attempts, easier and quicker with the SU-VEID device, therefore less exposure to risks.

Further, SU-VEID does not interfere with the normal blood return into the flash chamber of the catheter so its use does not obstruct a clinician's normal cues of entry into the vein. What it does is identify the precise time of entry into the lumen even if the patient's volume status is low and blood refill into the catheter is slow. This should allow the clinician to reduce "back wall" injury of the vessel and hence increase success.

Terms:

SU-VEID	Disposable sterile vein entry indicator device, FDA approved.
Success	The cannula is placed inside a vein and secured.
Fail	The procedure stopped due to a failure or the cannula found to be placed outside a vein right after completing the procedure, or a short time later.
IN-State	The needle's tip or the cannula's tip are inside a vein.
Sound of success	Fast beeps (8 per second) indicating in-vein Success state.
Sound of operation	Slow beeps (1 per second) indicating out of vein state
Half Detach	A temporary state while pulling the needle from a cannula or sliding forward the cannula on the needle for about an inch, the clinician normally ceases the detachment for a moment and hold (to see the blood upward in cannula) while the needle is still partially inside the cannula.
Full Detach	A state, where the needle is fully pulled out from the cannula.
AT	Angie Technologies Ltd.
SPIV	Short Peripheral Intravenous
DVA/DIVA	Difficult Intravenous Access

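### Harms are collected without prompting, at no set time and with no planned analysis, so the trial could not support direct or comparative safety statements

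*Combined protocol and SAP*

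**What the plan says.** The Risk section gives one sentence on collecting harms: "Any adverse reactions reported by subjects or noted by study personnel will be recorded and reported". No list of events, time point, follow-up window, severity rule or assessor accompanies it. The Primary End Points, Secondary End Point and Statistical Analysis rows of the synopsis name first-attempt success, success within two sticks and procedural time. They name no harm and no safety analysis.

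The Study Groups row describes the subjects as "Pediatric patients in surgical pre-op (0-18 years old), requiring an I.V. catheter for surgery who are difficult venous access". A line printed under Exclusion in the Study Population row says that "placement of the IV will be done according to standard operating room procedures, which typically is after induction of general anesthesia by mask". It reads as a description of procedure rather than a criterion.

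The Clinical Background section lists what a misplaced catheter can lead to, "causing hematoma, tissue damage, phlebitis, extravascular drug administration, thrombosis, delay of treatment, catheter related blood stream infection and loss of vein". The Terms list at the end of the document defines a failed placement to include a cannula found outside the vein at once or soon afterwards, without saying how soon. The Benefit section says subjects may have the procedure "performed with less attempts, easier and quicker with the SU-VEID device, therefore less exposure to risks".

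**The concern.** Both channels in the Risk sentence are weak in this setting. Infants cannot report symptoms, and a child under general anesthesia cannot report pain or infiltration at insertion. That leaves what staff note unprompted. The Device Description says the device beeps and lights, so the inserter knows the arm and others within earshot may too. Unprompted noting by people who know the arm can differ between arms.

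A low or zero count could then reflect the method of collection as much as the device, and a difference between arms could reflect who was looking. Harms that nobody asked about cannot be reliably reconstructed after the trial.

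**Working it through.** The plan gives no figure for harms, so there is none to reproduce. Its one calculated figure, the sample size, concerns first-attempt success and does not bear on this point.

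**Step 1: what the plan would record.**

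| Event | Route in the plan |
|---|---|
| Cannula found outside the vein soon after placement | Failure definition in the Terms list; interval undefined |
| Hematoma, tissue damage | Risk sentence only |
| Staff needle-stick (named in the Background as a risk to be reduced) | Risk sentence at most; it speaks of adverse reactions |
| Phlebitis, thrombosis, blood stream infection | Risk sentence only; no observation is scheduled |

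Only the first row is tied to an outcome that both arms must have assessed.

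**Step 2: what the counts could show.** Inputs: 200 children per arm (Study Design row). The share of true events recorded, *f*, is not in the documents and is assumed. So are all true harm rates below.

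- Upper bound when no events are recorded among *n* = 200 (one-sided 95%): 1 − 0.05^(1/200) = 1.49% with full capture. With share *f* recorded, the bound on the true rate is 1.49% / *f*.
- Chance of recording no event in 200 when the true rate is 2%: (1 − 0.02 × *f*)^200.
- Power for two proportions, two-sided 0.05, pooled variance under the null: Φ{[|p1 − p2| − 1.96 × √(2p̄(1 − p̄)/200)] / √([p1(1 − p1) + p2(1 − p2)]/200)}, with both rates multiplied by *f*. For 10% vs 5% and *f* = 1: (0.05 − 1.96 × 0.02634) / 0.02622 = −0.062, so power is 47.5%.

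| *f* (assumed) | Upper bound if none recorded | Chance of none recorded, true rate 2% | Power, 10% vs 5% | Power, 20% vs 10% |
|---|---|---|---|---|
| 100% | 1.49% | 1.8% | 47.5% | 80.2% |
| 75% | 1.98% | 4.9% | 36.9% | 66.1% |
| 50% | 2.97% | 13.4% | 25.9% | 47.5% |
| 25% | 5.95% | 36.7% | 14.9% | 25.9% |

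**Step 3: unequal capture.** Suppose the true rate is 5% in both arms: 200 × 0.05 = 10 events each. If all are noted in one arm and half in the other, the recorded counts are 10 and 200 × 0.05 × 0.5 = 5. That is an apparent halving with no true difference.

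**The case against.** The strongest reply is that this is an efficacy trial of a device the plan calls FDA approved and low in risk, and that unsolicited reporting is an acceptable choice for it. The failure definition already records early misplacement in both arms, and misplacement is the event from which the Clinical Background derives its complications. The Risk sentence covers any reaction and has no cut-off at insertion, and older children can report once awake. The capture fractions are assumed, and the 1.49% bound would apply to any arm of 200.

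Much of this stands. The Risk sentence is not the sole route to every harm, and the plan's silence about staff roles after insertion does not show that nobody will look. The table illustrates scale and is not an estimate. Even with full capture, power is 47.5% for 10% vs 5% and 21.5% for 4% vs 2%, so better collection would not make this a powered safety comparison.

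The anesthesia line also needs care. Read literally as an exclusion, it would conflict with the statement that such placement is typical. If children were awake, the self-report argument would weaken for the older ones, but not for infants.

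Two further inferences are tempting and are not relied on here. The Clinical Benchmark remark that "IV placements failures are up to 50% of the time before the IVs reach the end of their intended use" is a general background figure on catheter failure, not a harm rate in these children. The Description of the SU-VEID mentions a slight pull-back guided by the signal, but nothing in the documents links it to harm.

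The reply does not supply a prompted, time-defined observation made the same way in both arms.

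**Conclusion.** The point holds in this form: no active, time-defined, arm-comparable collection of harms is specified, so the trial as written could not support direct or comparative safety statements. The primary endpoint is unaffected.

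The size depends on how incomplete recording would be, which the documents do not say. Zero recorded events among 200 SU-VEID children would be compatible with true rates up to 1.5% at full capture, and up to about 3.0% or 5.9% if half or a quarter of events were recorded. The conclusion also takes the anesthesia line to describe usual practice rather than an exclusion.

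A reader might go further and infer that the trial fails to back its own claims of low risk and reduced exposure to risk. The documents do not support that. The low-risk wording is a premise drawn from how the device is built and works, with an ISO 14971 assessment cited. The reduced-exposure wording is conditional and follows from fewer attempts and less time. The attempt and time endpoints bear on that reasoning and could support it indirectly. Neither statement is a planned conclusion of the trial.

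**What to change.** Replace the sentence in the Risk section with a short solicited checklist, identical in both arms:

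- **Items:** infiltration or extravasation, hematoma, early loss of the IV, staff needle-stick, other.
- **Times:** at securing, and once more at IV removal or discharge from recovery, whichever comes first.
- **Second entry:** made by existing staff other than the inserter, or taken from the routine IV-site record if the site confirms that one exists (the documents do not mention one).
- **Reporting:** counts by arm with confidence intervals, labelled descriptive. Limit any safety statement to this window, and state that phlebitis, thrombosis and blood stream infection are not assessed.

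Also define the interval left open in the failure definition, and clarify whether the anesthesia line under Exclusion is a criterion or a description of procedure.

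The cost is one short form and two brief entries per child (400 × 2 = 800 in all), a few minutes of data entry each child, with no added visits. More minor events will be recorded than under the present rule. The site must confirm who can make the second entry.

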### **Benefit**

Subjects may benefit by having the IV catheterization procedure performed with less attempts, easier and quicker with the SU-VEID device, therefore less exposure to risks.

Further, SU-VEID does not interfere with the normal blood return into the flash chamber of the catheter so its use does not obstruct a clinician's normal cues of entry into the vein. What it does is identify the precise time of entry into the lumen even if the patient's volume status is low and blood refill into the catheter is slow. This should allow the clinician to reduce "back wall" injury of the vessel and hence increase success.

Terms:

SU-VEID	Disposable sterile vein entry indicator device, FDA approved.
Success	The cannula is placed inside a vein and secured.
Fail	The procedure stopped due to a failure or the cannula found to be placed outside a vein right after completing the procedure, or a short time later.
IN-State	The needle's tip or the cannula's tip are inside a vein.
Sound of success	Fast beeps (8 per second) indicating in-vein Success state.
Sound of operation	Slow beeps (1 per second) indicating out of vein state
Half Detach	A temporary state while pulling the needle from a cannula or sliding forward the cannula on the needle for about an inch, the clinician normally ceases the detachment for a moment and hold (to see the blood upward in cannula) while the needle is still partially inside the cannula.
Full Detach	A state, where the needle is fully pulled out from the cannula.
AT	Angie Technologies Ltd.
SPIV	Short Peripheral Intravenous
DVA/DIVA	Difficult Intravenous Access
